8.5.1 Sample Size for Primary Endpoint #1 (Hypothesis One)

Primary endpoint #1: The observed difference in the mean excess weight loss (%EWL) at 52-weeks for the AT group and control group is > 25%. %EWL is defined as absolute weight loss divided by baseline excess weight and multiplied by 100. Excess weight will be determined from ideal body weights based on a BMI=25 kg/m2.

The first hypothesis presented is

 H_0 : $\mu_F - \mu_S < \delta$ versus H_A : $\mu_F - \mu_S \ge \delta$

Where μ_F is the observed %EWL for the **AT Group** and μ_S is the observed %EWL for **Control Group**. The value of δ is the clinically significant threshold value. Statistical differences between AT and Control groups will be evaluated by using a two-sample t-test. Using this hypothesis and the two-sample t-test, **Table 8.5.1** presents the sample size for the AT group (total in parenthesis) assuming a 2:1 randomization with the assumptions listed in the table. The significance level is 0.025 and the power = 90%.

Table 8.5.1 Requisite Sample Size for a 90% Power

			Observed Difference in Mean %EWL between AT and			
			Control			
Power	δ	Std.Dev	15%	20%	25%	30%
90%	10	15	286 (429)	74 (111)	34 (51)	20 (30)
		20	506 (759)	128 (192)	58 (87)	34 (51)
		25	790 (1185)	200 (300)	90 (135)	52 (78)
90%	15	15	Na	286 (429)	74 (111)	34 (51)
		20	Na	506 (759)	128 (192)	58 (87)
		25	Na	790 (1185)	200 (300)	90 (135)

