2.1 Primary Efficacy Endpoints (52-week)

The first effectiveness primary endpoint is the mean percent excess weight loss (%EWL) at 52-weeks. The hypothesis for the first primary effectiveness endpoint is that the difference in the mean percent excess weight loss (%EWL) at 52-weeks for the Aspiration Therapy (AT) group and Control group is at least 10%. %EWL is defined as absolute weight loss divided by baseline excess weight and multiplied by 100. Excess weight will be determined from ideal body weights based on a BMI=25 kg/m².

The second effectiveness primary endpoint is that at least 50% of the AT group at 52-weeks realizes a %EWL \geq 25%.

Both primary endpoints must be met for the study to be considered a success.

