8.1.1 Efficacy Endpoints

The first effectiveness primary endpoint is the mean percent excess weight loss (%EWL) at 52-weeks. The hypothesis for the first primary effectiveness endpoint is that the difference in the mean percent excess weight loss (%EWL) at 52-weeks for the Aspiration Therapy (AT) group and Control group is at least 10%. %EWL is defined as absolute weight loss divided by baseline excess weight and multiplied by 100. Excess weight will be determined from ideal body weights based on a BMI=25 kg/m².

The second effectiveness primary endpoint is that at least 50% of the AT group at 52-weeks realizes a %EWL \geq 25%.

Sections 8.51 and 8.52 provide analysis of the sample size to meet co-primary endpoint #1 and #2, respectively with a power of 90% for each endpoint.

Since these endpoints are co-primary, the sample size is determined by the largest sample sizes required of the two primary endpoints. Co-primary endpoint #1 requires a sample size of 87 subjects (59 AT/ 29) to have a superiority margin of 10% EWL with a power of 90%, assuming an observed difference of 25% EWL and a standard deviation of both groups of 20%. Co-primary endpoint #2 requires a sample size of 99 AT subjects to realize that at least 50% of the AT groups realize >25% EWL at 52 weeks with a power of 90%, assuming an observed rate of 66% and a standard deviation of 20% of the AT group.

Co-primary endpoint #2 requires the largest sample sizes of the two primary endpoints, hence, not accounting for subject drop-out, a total of 150 subjects are needed in a 2:1 randomization (100 AT + 50 Control).

Since the primary analysis will be based on an ITT analysis using multiple imputations to estimate the missing values, the importance of over enrolling to have the exact number of evaluable patients has been lessened. However, to mitigate the effect of the imputation methodology on the control group, an over enrollment of ~15% for both groups is being proposed for a total enrollment size of 175 subjects (117 AT/58 Control).

8.1.2 Discussion on Drop-out Rate and Standard Deviation.

As 9% of the AT subjects (1 out of 11) in the Feasibility Study did not complete 52-weeks, we believe a 10% drop-out rate of the AT subjects for the Pivotal Study is a reasonable assumption. An over-enrollment of 15% (e.g., 117 AT subject versus 99 required) should readily accommodate the anticipated drop-out rate.

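### Section 8.5.1 states co-primary endpoint #1 as an observed difference above 25 points of %EWL, contradicting the 10-point margin set in the Synopsis, 2.1 and 8.1.1

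*Protocol*

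**What the plan says.** The protocol describes the pass line for co-primary endpoint #1 in two ways.

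- **Ten points.** Section 2.1 states the hypothesis as "difference in the mean percent excess weight loss (%EWL) at 52-weeks for the Aspiration Therapy (AT) group and Control group is at least 10" per cent. The Synopsis and 8.1.1 repeat it. Section 8.1.1 then sizes the endpoint "to have a superiority margin of 10% EWL with a power of 90%, assuming an observed difference of 25% EWL", with "a standard deviation of both groups of 20" per cent. Here 10 is the margin and 25 is the assumed effect.
- **Twenty-five points.** Section 8.5.1, which sits under the protocol's own analysis-plan heading (8.5), opens by giving primary endpoint #1 as "The observed difference in the mean excess weight loss (%EWL) at 52-weeks for the AT group and control group is > 25" per cent. Nothing in that section labels 25 as an assumption.

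Section 8.5.1 then writes H0 and HA in terms of δ, with both μ terms defined as observed %EWL. On the size of δ it says only "The value of δ is the clinically significant threshold value". Table 8.5.1 has rows for δ = 10 and δ = 15. The test is a two-sample t-test, and "The significance level is 0.025 and the power = 90" per cent.

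Section 2.1 makes trial success depend on meeting both co-primary endpoints.

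**The concern.** A reader who takes 8.5.1 at its word would declare endpoint #1 failed unless the point estimate exceeded 25. A reader who takes 2.1 and 8.1.1 would test against a margin of 10. Since both co-primaries must be met, the choice can decide whether the trial succeeds.

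The sentence is hard to pass over as loose wording about planning. Section 8.5.2 uses the same lead-in for endpoint #2, and there it introduces the real success criterion (at least 50% of AT subjects); its planning value of 66% appears in that section only as a table column. By that parallel, 8.5.1 presents 25 as the criterion. Defining μ as an observed quantity also pulls towards a rule on the sample estimate rather than a test about population means.

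If the conflict is left until data are available, whichever line is used can be challenged as having been chosen for its result.

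**Working it through.** **Inputs.** Margin 10, assumed difference 25, SD 20 in both groups, planned enrolment 117 AT and 58 Control (8.1.1); significance level 0.025, power 90%, 2:1 allocation, two-sample t-test (8.5.1); assumed drop-out 10% AT and 20% Control (8.1.2).

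**1. Reproduce the stated sample size.** The effect to be detected beyond the margin is 25 − 10 = 15. With one-sided α = 0.025 and 2:1 allocation:

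n(Control) = SD² × (1 + 1/2) × (1.960 + 1.282)² / 15² = 400 × 1.5 × 10.51 / 225 ≈ 28.02, rounded up to 29.

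That gives 29 Control and 58 AT, total 87, as in Table 8.5.1 and the total in 8.1.1. (Section 8.1.1 prints 59 AT with 29, which adds to 88; the table's 58 is the figure that fits.) The noncentral-t calculation also gives 58 and 29, with power 90.3%, and it matches all twelve δ = 10 cells of the table. A two-sided 0.025 level would need 68 AT and does not reproduce the figure. So the sizing treats 10 as the margin and 25 as the assumed effect.

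**2. Where the margin-10 test is met at planned enrolment.**

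SE = 20 × √(1/117 + 1/58) = 3.21; df = 173; t(0.975) = 1.974.

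Observed difference needed = 10 + 1.974 × 3.212 ≈ 16.3 points.

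**3. Chance of success under each rule (117 and 58, SD 20, no drop-out).**

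| True difference | Test against δ = 10 | Observed difference > 25 |
|---|---|---|
| 25 | 99.6% | 50% |
| 20 | 87.2% | 6.0% |

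The first column is noncentral-t power with noncentrality (true − 10)/3.212, that is 4.67 and 3.11. The second is 1 − Φ((25 − true)/3.212), that is 1 − Φ(0) and 1 − Φ(1.557). The 50% does not depend on sample size: an unbiased estimate falls above its true value half the time.

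**4. How often the two rules disagree.** They disagree when the observed difference lies between about 16.3 and 25. At a true difference of 25 this has probability about 99.6 − 50 = 49.6%; at 20, about 87.2 − 6.0 = 81.2%.

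**5. Allowing for drop-out.** 117 × 0.90 ≈ 105 and 58 × 0.80 ≈ 46 give SE = 20 × √(1/105 + 1/46) = 3.54. The margin-10 test is then met at about 17.0 points and has 98.8% power at a true difference of 25. The literal rule stays at 50%.

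**The case against.** The best defence is that the intended rule can be recovered. Three statements of the hypothesis, the named margin in 8.1.1 and the 87-subject sizing all agree on 10. Section 8.5.1 is headed as a sample-size section, and Table 8.5.1 uses the term observed difference for its planning scenarios, of which 25 is one. The sentence looks like the planning value carried into the endpoint line. That explains the likely origin and stands as far as it goes. It does not remove the conflict: 8.5.1 is where the hypothesis, test and significance level are set, and it labels 25 as the endpoint.

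A reader might infer more than the document supports:

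- *That the margin is fixed nowhere.* Only the H0/HA line in 8.5.1 leaves δ open; 2.1 and 8.1.1 give 10.
- *That 15 is a rival margin.* No prose adopts it. The δ = 15 rows belong to a planning grid that also varies the SD and the difference, and 8.1.1 picks the cell with δ = 10, SD 20 and difference 25.
- *That 2.1 allows success on a point estimate of 10 or more, with a 50% error rate at the margin.* Section 8.5.1 specifies a t-test against δ at 0.025, so that rule is not the one planned.
- *That a rule of more than 25 could never reach 90% power.* It would at a true difference of about 25 + 1.282 × 3.212 ≈ 29.1. The feasibility means in the protocol's introduction, 49.0 and 14.9 (a gap of 34.1, with only three controls), would give about 99.8%. The shortfall is at the assumed difference of 25. The 90% in 8.1.1 is claimed for the margin-10 test, which achieves it.

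**Conclusion.** Wrong as written. The protocol contains two incompatible pass lines for a co-primary endpoint: a test against a 10-point margin, and one sentence in 8.5.1 requiring an observed difference above 25. The sizing supports the first. The practical gap is the range from about 16.3 to 25 observed points, where the trial would pass endpoint #1 on one reading and fail on the other; at the protocol's own assumed difference, about half of all trials would land there.

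These figures assume SD 20 in both groups, a one-sided 0.025 t-test and full enrolment of 117 and 58. The assumed drop-out moves the lower edge only to about 17.0 points. The finding concerns the statement of the criterion; the sample size for this endpoint is adequate under the 10-point margin.

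**What to change.** In 8.5.1, replace the endpoint sentence with:

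> Success on endpoint #1 = lower limit of the two-sided 95% CI for the AT minus Control difference in mean %EWL exceeds 10 points (δ = 10).

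This is equivalent to the one-sided 0.025 test that the table reproduces under, and it fits the 5% level for tests and intervals in 8.2. In the same section:

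- write δ = 10 into H0 and HA;
- define the μ terms as population means;
- label 25% as the planning assumption;
- label the δ = 15 rows as scenarios only.

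Use the same criterion in the Synopsis, 2.1 and 8.1.1. The cost is a wording amendment, best made before any comparative 52-week results are seen. Sample size, test and enrolment stay as they are.

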8.5.2 Sample Size for Primary Endpoint #2 (Hypothesis Two)

Primary endpoint #2: At least 50% of the AT group at 52-weeks realizes a %EWL > 25%.

Hypothesis:

H₀: $\pi_{AT} \le 50\%$ H_a: $\pi_{AT} > 50\%$

Where π_{AT} is the proportion of patients who have a % EWL \geq 25% for the Aspiration Therapy group.

Using this hypothesis and the Fisher's exact test, the following table presents the sample size for the AT group with the assumptions listed in the table. The significance level is 0.025 and the power = 90%.

Table 8.5.2 Sample Size for Hypothesis Two

Power	Expected Proportion					
	55%	60%	65%	66%	67%	70%
90%	1047	259	113	99	87	62

8.5.3 Sample Size for Adverse Event Detection

Given the sample size for the AT device, **Table 8.5.3** shows the probability of detecting at least one adverse event with the given rate.

Table 8.5.3 Probability of Observing At least One AE

Probability	Probability of		
of an AE	Observing		
	at least one AE		
1%	27%		
2%	61%		
3%	81%		
4%	91%		
5%	97%		
6%	98%		
7%	99%		
8%	100%		
9%	100%		
10%	100%		

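### Table 8.5.3 does not give the probability of seeing at least one adverse event for any sample size: it prints 27% at a 1% rate, where 117 AT subjects give 69%

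*Protocol*

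**What the plan says.** Section 8.5.3 opens with "Given the sample size for the AT device" and says that the table "shows the probability of detecting at least one adverse event with the given rate". The table title repeats the quantity: "Probability of Observing At least One AE". The printed values for true rates of 1% to 10% are 27, 61, 81, 91, 97, 98, 99, 100, 100 and 100%. The section does not state the n behind them.

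Section 8.1.1 gives several candidates for the AT sample size:

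- 59, from the first co-primary endpoint: "Co-primary endpoint #1 requires a sample size of 87 subjects (59 AT/ 29".
- 99, from the second: "Co-primary endpoint #2 requires a sample size of 99 AT subjects".
- 100, before over-enrollment: "a total of 150 subjects are needed in a 2:1 randomization (100 AT + 50 Control".
- 117, the planned enrollment: "a total enrollment size of 175 subjects (117 AT/58 Control".

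**The concern.** The label is unambiguous, and the quantity it names has a one-line formula. A value of 27% at a 1% rate is visibly too small for an arm of about 100 or more subjects, where the expected count is already about one event.

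Safety is half of the study objective in Section 2.0, and Section 2.3 names the incidence of adverse and serious adverse events as the safety outcomes. Table 8.5.3 is the only place where the protocol quantifies how likely it is to see a harm of a given frequency. A reader needs that figure to judge what it means if an event is never observed. As printed, a harm with a true rate of 1% would go unseen with probability 73% (100-27). The trial is meant to support a premarket approval application, so this reading matters.

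**Working it through.** **Inputs.** The rates p and the printed probabilities come from Table 8.5.3. The AT sample sizes 59, 99, 100 and 117 come from Section 8.1.1. I also use about 105, which is 117 × 0.90 with the 10% AT drop-out assumed in Section 8.1.2.

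**Step 1: try to reproduce the table as labelled.** With X the number of subjects with the event, P(X≥1) = 1-(1-p)^n. Solving for n gives n = ln(1-P)/ln(1-p):

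| Rate p | Printed P | Implied n |
|---|---|---|
| 1% | 27% | 31.3 |
| 2% | 61% | 46.6 |
| 3% | 81% | 54.5 |
| 4% | 91% | 59.0 |
| 5% | 97% | 68.4 |
| 6% | 98% | 63.2 |
| 7% | 99% | 63.5 |

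Rounding does not explain the spread. If 27% stands for anything from 26.5% to 27.5%, the first row needs n between 30.6 and 32.0. If 61% stands for 60.5% to 61.5%, the second row needs n between 46.0 and 47.2. The ranges do not overlap, so no single n gives even the first two rows. In a search over every n from 10 to 299, the best fit (n=43) still misses by 8 points.

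**Step 2: compute the labelled quantity at the protocol's own sample sizes.** For example, at n=117 and p=1%, 1-0.99^117 = 0.691.

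| Rate | Printed | n=59 | n=99 | n=100 | n=117 | Printed minus n=117 (points) |
|---|---|---|---|---|---|---|
| 1% | 27% | 44.7% | 63.0% | 63.4% | 69.1% | -42 |
| 2% | 61% | 69.6% | 86.5% | 86.7% | 90.6% | -30 |
| 3% | 81% | 83.4% | 95.1% | 95.2% | 97.2% | -16 |
| 4% | 91% | 91.0% | 98.2% | 98.3% | 99.2% | -8 |
| 5% | 97% | 95.2% | 99.4% | 99.4% | 99.8% | -3 |

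Allowing for drop-out does not help: at about 105 subjects the first three rows are 65.2, 88.0 and 95.9%.

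**Step 3: look for what was computed.** The probability of at least two events is P(X≥2) = 1-(1-p)^n - n·p·(1-p)^(n-1). At n=100 and p=1% this is 1 - 0.366 - 0.370 = 0.264. Over all ten rows:

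| n | P(X≥2) at rates 1% to 10% |
|---|---|
| Printed | 27, 61, 81, 91, 97, 98, 99, 100, 100, 100 |
| 100 | 26.4, 59.7, 80.5, 91.3, 96.3, 98.5, 99.4, 99.8, 99.9, 100.0 |
| 117 | 32.7, 68.1, 86.9, 95.0, 98.2, 99.4, 99.8, 99.9, 100.0, 100.0 |

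At n=100 the largest deviation from the printed column is 1.3 points. At n=101 or 102 it is 0.8 points. At n=117 it is 7.1 points.

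**Step 4: what a zero count means at n=117.** A harm with a true rate of 1% is missed with probability 0.99^117 = 31%, not 73%. The one-sided 95% upper limit for the rate after zero events is 1-0.05^(1/117) = 2.5%.

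**The case against.** The arithmetic is hard to contest, but its weight can be questioned.

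- **Nothing in the design rests on this table.** Section 8.1.1 sets enrollment from the co-primary endpoints, Section 8.4 tabulates events and applies Fisher's exact test, and Section 7.4 ties any halt to an identified risk, not to a detection probability. This stands, and it is why the point is a correction to make and not an obstacle to the trial.
- **The error is in the cautious direction.** The printed values are too low, so a reader would draw less reassurance from a zero count than the data warrant. This also stands. The gap is large only in the 1% to 3% rows and is about 3 points or less from 5% upward.
- **The cause is inferred.** The protocol mentions neither at least two events nor the n used. The numerical fit is close, but it shows only what the column is consistent with.
- **117 is not the only defensible n.** Section 8.5.3 does not give the number, Section 8.5 defines the analysis population as subjects who undergo treatment, and Section 5.4.1 discharges those whose tube cannot be placed. The number exposed may fall below 117. That is a reason to state the n. It does not rescue the table, because no n reproduces it and the 1% row is 63% to 69% across 99 to 117 subjects.

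**Conclusion.** The concern holds. As probabilities of at least one adverse event, the figures in Table 8.5.3 match no sample size in the trial and are inconsistent among themselves. Against the planned 117 AT subjects they are too low by 42, 30 and 16 percentage points at rates of 1%, 2% and 3%. Against 99 subjects the shortfalls are 36, 26 and 14 points (63.0-27, 86.5-61 and 95.1-81, rounded).

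The calculation assumes independent subjects with a common event rate and counts subjects with at least one occurrence. The conclusion that no n fits does not depend on which sample size was intended. The most plausible origin is a calculation for at least two events at roughly the size before over-enrollment, and that remains an inference. The error is conservative and leaves the efficacy sample size and all tests untouched. It should still be corrected, because it misstates the protocol's only figure for detecting harms.

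**What to change.** Replace the column in Table 8.5.3 with 1-(1-p)^117 and state the n in the table title: 69, 91, 97, 99, 99.8 and 99.9% at rates of 1% to 6%, and 100% after rounding from 7%. If the number of subjects actually exposed is expected to be lower, use that number and say so.

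If at least two events was the intended criterion, change the title, header and sentence to say so and recompute at n=117: 33, 68, 87, 95 and 98% at rates of 1% to 5%. Relabelling the existing figures without recomputing would leave them up to 7 points off.

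One further sentence would be useful though not required: zero events in 117 subjects excludes a rate above about 2.5% (one-sided 95%).

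The cost is one replaced table, with no change to enrollment, endpoints or analyses.

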8.5.4 Secondary Efficacy Endpoints

The percent change from baseline will be calculated for all major time points and the results will be summarized for each group. Within treatment group differences will be tested using a Students T-test for paired samples on the percentage change from baseline at each study visit. Difference between treatment groups will be tested by using the two-sample t-test or Wilcoxon Test whenever appropriate.

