This is a multi-center, randomized, controlled, open-label, 52-week trial to support FDA premarket approval with additional long-term safety and efficacy monitoring of the treatment group for post market reporting and publication purposes. Eligible subjects will be randomized in a 2:1 (treatment: control) ratio to treatment with the Aspiration Therapy (n=117) or lifestyle therapy (behavior education, diet and exercise) program (n=58). The AspireAssist™ Aspiration Therapy System involves percutaneous endoscopic placement of a gastric device that permits aspiration of a portion of stomach contents after meals, in conjunction with lifestyle therapy.

Aspiration Therapy subjects who lose and maintain at least 10% weight loss from baseline will be given the option to continue in the study for an additional four years after the 52-weeks of therapy.

Primary Outcomes:

The first effectiveness primary endpoint is the mean percent excess weight loss (%EWL) at 52-weeks. The hypothesis for the first primary effectiveness endpoint is that the difference in the mean percent excess weight loss (%EWL) at 52-weeks for the Aspiration Therapy (AT) group and Control group is at least 10%. %EWL is defined as absolute weight loss divided by baseline excess weight and multiplied by 100. Excess weight will be determined from ideal body weights based on a BMI=25 kg/m².

The second effectiveness primary endpoint is that at least 50% of the AT group at 52-weeks realizes a %EWL \geq 25%.

Both primary endpoints must be met for the study to be considered a success.

Secondary Outcomes (at 52-weeks)

i) Mean percent absolute weight loss in AT compared to Control group, ii) proportion of subjects who achieve ≥10% absolute weight loss in AT compared to Control group, iii) mean percent change serum lipids (triglyceride, HDL-cholesterol and LDL-cholesterol concentration) in the AT group compared to the control group; iv) mean percent change in systolic and diastolic blood pressures in the AT group compared to the control group; v) "Impact of Weight on Quality of Life" (IWQOL) questionnaire; vi) change in mean hemoglobin A1C (only subjects with T2 diabetes at baseline) , vii) percent procedural success (defined as successful endoscopic placement of the A-Tube) in all subjects undergoing endoscopy; viii) mean percent change in medications

Safety Outcomes:

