2.2 Secondary Efficacy Endpoints (52-week)

- i) Mean percent absolute weight loss in the AT group compared to the Control group
- ii) Proportion of subjects who achieve ≥10% absolute weight loss in the AT group compared to the Control group

The percent change in the AT Group compared with the percent change in the Control Group will be assessed for the following variables:

- iii) Serum triglyceride, HDL-cholesterol and LDL-cholesterol concentration
- iv) Systolic and diastolic blood pressures
- v) "Impact of Weight on Quality of Life" (IWQOL) questionnaire
- vi) Hemoglobin A1C (for subjects with T2 diabetes at screening only)
- vii) mean percent change in medications

In the AT group only:

viii) Procedural success defined as successful endoscopic placement of the A-TubeTM in all subjects undergoing endoscopy

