8.2 Statistical Methods

Tabulation of summary statistics, graphical presentations, and statistical analyses will be performed using SAS® software. Where not otherwise specified, the last pre-treatment (i.e. for treatment group, this is prior to the initiation of therapy) observation will be used as baseline for calculating post-treatment changes from baseline. The primary presentations and analyses will be based on data pooled across study centers. Relevant summaries for individual centers, or combinations of centers, may be presented for primary data. All testing and confidence intervals will use a significance level of 5%.

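### The within-group t-test on percentage change (Section 8.5.4) does not hold its 5% level for no change when a measure varies within subjects, as triglycerides may; the between-group endpoint is unaffected

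*Protocol*

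**What the plan says.** Section 8.5.4 fixes the within-group analysis of the secondary endpoints: "Within treatment group differences will be tested using a Students T-test for paired samples on the percentage change from baseline at each study visit". The next sentence covers the comparison of arms: "Difference between treatment groups will be tested by using the two-sample t-test or Wilcoxon Test whenever appropriate". The rank test is offered only there. No log transform is mentioned for either comparison.

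Section 2.2 defines the contrast of interest between arms: "The percent change in the AT Group compared with the percent change in the Control Group will be assessed for the following variables". The list includes "Serum triglyceride, HDL-cholesterol and LDL-cholesterol concentration". The Synopsis describes the same item as "mean percent change serum lipids (triglyceride, HDL-cholesterol and LDL-cholesterol concentration) in the AT group compared to the control group".

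Section 8.2 takes the last pre-treatment observation as baseline unless otherwise specified, and sets the level for every test at five percent: "All testing and confidence intervals will use a significance level of 5". Tables 1 and 3 place lipid panels at screening, week 28 and week 52 in both arms. Section 8.1.3 says that secondary results are for listing in tables and are not proof of efficacy.

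**The concern.** A within-group test is read as asking whether a group's values moved from baseline. The planned test asks whether the average of each subject's (follow-up − baseline)/baseline is zero. These are different questions when single measurements vary within a subject. A rise from 100 to 150 counts as +50%, while the reverse move from 150 to 100 counts as −33%. A group in which such moves balance exactly has a positive mean percentage change.

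At stake are the single-arm p-values that accompany the lipid tables. For a measure that varies enough, they can mark a rise where nothing happened and fail to mark a modest real fall. A larger group does not help: the offset is fixed while the standard error shrinks, so the larger AT arm is affected more than the Control arm.

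**Working it through.** **Inputs from the protocol**
- Group sizes, Section 8.1.1: "total enrollment size of 175 subjects (117 AT/58 Control".
- AT drop-out, Section 8.1.2: "we believe a 10% drop-out rate of the AT subjects for the Pivotal Study is a reasonable assumption". Completers: 117 × 0.90 = 105.3, about 105.
- Control drop-out of 20%, Section 8.1.2. Completers: 58 × 0.80 = 46.4, about 46.
- Level 5%, taken as two-sided (Section 8.2).

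**Assumptions, not in the protocol**
- Values are log-normal, with independent within-subject variation at the two visits.
- Within-subject CV is shown from 5% to 30%.

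**Formulas.** Let s² = ln(1 + CV²). The follow-up/baseline ratio is R = (1 − f) × exp(N(0, 2s²)), where f is the true proportional fall.
- Mean percentage change = 100 × [(1 − f)(1 + CV²) − 1].
- With f = 0 this is 100 × CV²: +1% at CV 10%, +4% at 20%, +9% at 30%.
- With f = 0, SD(R) = (1 + CV²) × √[(1 + CV²)² − 1].

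**Hand check, CV 20%, n = 105, no change.** SD = 1.04 × √(1.0816 − 1) = 0.297. Shift in the t statistic = 0.04 × √105 / 0.297 = 1.38. The chance of exceeding 1.96 is about P(Z > 0.58) = 28%. Simulation gives 26%; skewness accounts for the difference.

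**No true change: rejection rate of the two-sided 5% test** (simulation, 20,000 runs per cell)

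| CV | Planned test, n = 105 | Planned test, n = 46 | Log ratio, either n |
|---|---|---|---|
| 5% | 6% | 6% | 5% |
| 10% | 10% | 7% | 5% |
| 15% | 17% | 9% | 5% |
| 20% | 26% | 12% | 5% |
| 25% | 37% | 16% | 5% |
| 30% | 48% | 20% | 5% |

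The log-ratio test reproduces the plan's nominal 5%; the planned test does not. At n = 105 and CV 20%, 26.1% of runs show a significant rise and 0.1% a significant fall. Repeat simulations differ by about one percentage point.

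**True 10% fall, n = 105: power to show a fall**

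| CV | Mean percentage change, 100 × [0.9(1 + CV²) − 1] | Planned test | Log ratio |
|---|---|---|---|
| 15% | −8.0% | 98% | 100% |
| 20% | −6.4% | 68% | 97% |
| 25% | −4.4% | 28% | 87% |
| 30% | −1.9% | 9% | 73% |

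Larger falls are mostly still found: with n = 117 and CV 30%, a true 20% fall is detected 93% of the time.

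**Between-group comparison, 105 versus 46.** With no change in either arm, the two-sample t-test on percentage change rejects about 5% of the time at every CV. With a 10% fall in AT only, power at CV 15/20/25/30% is about 80/55/39/29% on percentage change and 80/56/40/30% on the log ratio. The expected difference in mean percentage change is −10% × (1 + CV²), that is −10.2% to −10.9% over the same range.

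**The case against.** The strongest reply is that nothing important rests on this test. The endpoint in Section 2.2 and the Synopsis is the comparison of arms, and both arms carry the same offset. That stands: the between-group test keeps its level and logs add nothing to it. A reader might infer that the triglyceride endpoint itself is biased; the check above shows otherwise. Section 8.1.3 also keeps secondary results out of any claim, and for triglycerides the error points to a rise, so it cannot create a false benefit.

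Second, the arithmetic mean percentage change is what the Synopsis names, and the sample mean estimates it correctly. That stands too. It would be too strong to call the planned group means wrong; the narrower point is that zero on that scale does not mean an unchanged distribution.

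Third, the size depends on a CV that the protocol does not give. This also stands. A reader might infer that the test always rejects far above 5% and generally misses a 10% fall. At CV 5% the excess is about one percentage point, and at CV 15% the fall is still found 98% of the time. Nor does the protocol show that triglycerides are the most variable measure listed.

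Fourth, the test applies at each visit, but lipids have only two post-baseline panels in the first year, so few p-values are involved.

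The reply does not remove the defect. Section 8.5.4 commits to this test without a rank or log alternative, so it is a stated choice rather than a detail left to an analysis plan. The direction of the offset needs no outside figure. Descriptive status does not make a nominal 5% p-value accurate.

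**Conclusion.** The point holds in a limited form. As written, the within-group test in Section 8.5.4 does not test no change at 5%. Under the log-normal model with 105 AT completers, it rejects about 10% at an assumed CV of 10%, rising to about 48% at CV 30%, almost always as an apparent rise. With 46 Controls the range is about 7% to 20%. The loss of power for a true 10% fall is negligible at CV 15%, material at 20% and severe at 30%. If the real within-subject CV is near 5%, the matter can be ignored.

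The between-group endpoint, both primary endpoints and the labeling claims are not affected. Priority: minor, a change to consider.

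**What to change.** In Section 8.5.4, for triglycerides (and the other lipids for consistency), carry out the within-group paired t-test on log(follow-up/baseline). Report the back-transformed geometric mean percentage change with its 95% confidence interval beside the planned arithmetic mean percentage change. Leave the between-group comparison and the endpoint definitions in Section 2.2 and the Synopsis as they are.

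A paired t-test on absolute change would also restore the level (4.7% to 5.2% in the same simulations), but its result would not be on the percentage scale used in the tables.

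Cost: one sentence of analysis wording, one extra summary line per lipid and a table footnote explaining the two means. No new data, visits or subjects are needed.
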